5.1 Analysis Populations

One control population will be considered in primary analyses: the historical control population. The historical control population includes all subjects who attended ChristianaCare during the eligibility period and who satisfy all eligibility criteria.

The historical control arm will be the control population for primary and alternative analysis of the primary, secondary and exploratory endpoints.

Seven subject populations will be considered in the analyses: an Intent-to-Treat (ITT) population, a modified ITT population, a completer(s) population, a compliant completers population, a non-intervention completers population and a safety population. The completers, compliant completers, non-intervention completers and modified ITT populations are subsets of the ITT population.

The ITT population includes all historical subjects selected and all prospective patients enrolled regardless of whether or not the co-primary outcomes were observed, or in the prospective arm, any PreTRM test result has been generated or intervention consent has been signed. Subjects with missing outcomes will be handled as described in the missing data sensitivity analyses.

The modified ITT (mITT) population includes all subjects for whom both co-primary outcomes are known; and who have either been selected for the historical control group, received a not-higher-risk PreTRM® test result, or consented to and initiated treatment before 24^{0/7} weeks gestation after receiving a higher risk PreTRM® test result.

The completers population includes subjects for whom both of the co-primary outcomes are known, and, in the prospective arm, for whom a PreTRM® test result was generated.

The compliant completers population includes ITT subjects who have missed no more than 20% of daily doses for both low-dose aspirin and vaginal progesterone, and participated in weekly care management calls with no more than 20% missed weeks.

The non-intervention completers population includes all ITT subjects who received a higher-risk PreTRM® test result but neither consented to nor initiated treatment before 24^{0/7} weeks gestation.

The safety population includes all eligible subjects who gave consent to participate in the study and attempted a blood draw for the PreTRM® test, regardless of receipt of study interventions.

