Descriptive statistics on baseline covariates will be compared between the prospective arm and historical controls. This analysis includes covariates prespecified for both the primary and alternative analyses. If we can obtain information on some of the covariates that affect exposures and decisions to participate, we can assess our ability to reduce bias. Sociodemographic factors such as education and age are often considered in this role.

It is common that the basic characteristics may not be balanced between the prospective cohort and historical cohort groups. We will examine the potential sources of bias and address them with a classical and common technique—adjusting by covariates.

While an easy to implement strategy to control for selection bias in propensity scoring is to adjust for factors that can break the biasing paths linking the exposure and the outcome, regression with covariates benefits from adjustment for independent predictors of the outcome. We expect that adjustment for independently predictive covariates can result in decreased selection bias and increased precision.

The factors which impact the effect of intervention through selection and epoch biases will be assessed to demonstrate how well they address confounding in the analysis. Model selection techniques will be used to demonstrate an optimized model. Although a minimum set of covariates is prespecified for use in addressing confounding, there may be an advantage in exploratory analyses to using a staged approach in which groups of covariates are introduced sequentially leading to progressively greater adjustment. Using random forest and other machine learning methods, we will provide insight into which covariates have relatively greater influences on effect estimates, permitting comparison with known or expected associations or permitting the identification of possible mediator and/or intermediate variables.

In alternative and exploratory analyses, the propensity score model will model the propensity score: predicted probability of a participant who will be placed in the prospective group, via running logistic regression: the dependent variable,

$y=1$, if prospective group;

$y=0$, if historical group.

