The propensity score model will be derived from logistic regression using the key clinical covariates available at the gestational age of PreTRM® blood draw in the historical cohort, as well basic demographic characteristics. The variables used to generate propensity scores are specified above.

The performance of the propensity score model will be evaluated by AUC/ROC c-index; potential interaction terms or high degree of terms may be included to improve the performance of the propensity model. We will obtain an estimation for the propensity score: predicted probability (p).

With propensity score methods, we will check whether covariates are balanced across the prospective and historical cohorts. We can examine the distribution of propensity score between groups. We will assess covariate balance between groups using p-value for comparison of two group, as well absolute standardized mean difference (ASMD), with an ASMD <0.1 indicating good balance.

We propose Inverse Propensity score Weighting (IPW) method for the alternative analysis. IPW is a statistical technique for calculating statistics standardized to a pseudo-population different from that in which the data was collected. After obtaining propensity score, we define for the prospective arm:

$$IPW = \frac{1}{PS}; \quad IPW = \frac{1}{PS}; \quad \text{for historical controls: } IPW = \frac{1}{1-PS}.$$

$IPW = \frac{1}{1-PS}$. To avoid the IPW method's instability to extremes of propensity among participants with high propensity score weights with undue influence the results, we will use truncated scores and weights: 1) below the 1st or 5th percentile and above the

99th or 95th percentile; resulting in weights between reasonable intervals for all participants; 2) truncating propensity score <0.001 or >0.999.

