As exploratory analyses, the primary and alternative analyses will be replicated using the completers population with treatment covariates. Covariates for treatment modalities inclusive of use of aspirin or progesterone, will be included in the analyses if showing record of use between LMP and delivery in both the prospective arm and historical controls. Subjects with missing data for required variables will be excluded from the analyses. Subjects in the higher-risk group accepting interventions will be compared to non-intervention completers and to historical controls using descriptive statistics as described above. If use of any treatment is significantly associated with variables specified for the alternative analysis, this analysis will be repeated with inclusion of such variables as covariates in the analysis. Subjects with missing data for required variables will be excluded from this analysis.

As an exploratory analysis, the primary and alternative analyses will be replicated using the compliant completers population plus the not-higher-risk group as the preterm prevention arm for comparison to historical controls. Additional subgroup analysis of the compliant completers population will apply the primary, secondary and exploratory endpoints to subjects compliant with each component of the intervention versus all other compliant completers, and versus non-intervention completers. If compliance with any

treatment is significantly associated with variables specified for the alternative analysis, this analysis will be repeated with inclusion of such variables as covariates in the analysis. Subjects with missing data for required variables will be excluded from this analysis.

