The use of antenatal corticosteroids will be assessed in relation to primary, secondary and exploratory endpoints, and will be compared between the preterm prevention arm and historical controls, and between higher risk and not higher risk subjects in the preterm prevention arm. Optimal timing of dosing of antenatal corticosteroids is herein defined as 2 to 7 days (inclusive) prior to delivery at less than 37 weeks of gestation. Use of antenatal corticosteroids will be expressed as a binary variable: were steroids given in the optimal interval between dose and delivery? Significance of interaction between optimally timed use of antenatal corticosteroids and the specified treatment groups will be assessed in regression as an interaction term: (binary variable) * group. This analysis will be performed without adjustment, adjusted for covariates as specified for the primary analysis, and adjusted via propensity scoring as specified for the alternative analysis. Missing values will be addressed as previously specified for exploratory analyses: by omission of subjects with missing values and by replicating the analysis with multiple imputation of missing values.

Primary, secondary and exploratory endpoints will be assessed in the prospective portion of the mITT population as dependent responses to nonrandom quantitative assignment of treatment⁴². The independent quantitative assignment variable will be the PreTRM® risk score. The functional relationship between endpoints and the risk score will be estimated for the prospective arm. A discontinuity at the intervention threshold in the relationship between outcome and risk score observed in the prospective arm will demonstrate intervention effect, measured as the estimated magnitude of the discontinuity and re-assessed as the estimated risk-score dependent difference between compliant completers and non-intervention completers. As this analysis involves only prospective subjects, it is independent of any selection biases or epoch effects present in comparisons of the prospective arm relative to historical controls. To adjust for any biases present within the

prospective arm, the analysis will be performed without adjustment, adjusted for covariates as specified for the primary analysis, and adjusted via propensity scoring as specified for the alternative analysis.

The primary, secondary and exploratory endpoints will be applied to comparisons within the mITT population.

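### The propensity score assigned to the compliant versus non-intervention completers contrast models prospective versus historical membership, so it cannot balance those two groups

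*SAP*

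**What the plan says.** SAP section 5.7 plans an analysis of outcome against PreTRM risk score, using prospective women only. A jump at the intervention threshold is taken as the treatment effect and is then "re-assessed as the estimated risk-score dependent difference between compliant completers and non-intervention completers". To handle bias inside the "prospective arm, the analysis will be performed without adjustment, adjusted for covariates as specified for the primary analysis, and adjusted via propensity scoring", with the scoring taken from the alternative analysis.

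Section 5.3 fixes what that scoring is. It opens "In alternative and exploratory analyses, the propensity score model will model the propensity score" and defines the score as the "predicted probability of a participant who will be placed in the prospective group, via running logistic regression", with y = 1 for prospective and y = 0 for historical subjects. Prospective women are weighted 1/PS and historical controls 1/(1 − PS). On diagnostics it says "we will check whether covariates are balanced across the prospective and historical cohorts", with an absolute standardized mean difference below 0.1 as the mark of good balance.

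Section 5.1 defines compliant completers by adherence to the interventions. The non-intervention completers population "includes all ITT subjects who received a higher-risk PreTRM® test result but neither consented to nor initiated treatment before" 24 weeks 0 days. Section 5.4 defines the alternative analysis as covariate regression plus inverse-propensity weighting. No model of accepting, or of complying, versus declining appears anywhere in the SAP.

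**The concern.** A propensity score balances the two groups that its dependent variable separates. Here the dependent variable separates cohorts, while the contrast is between women who took up the interventions and women who did not. The named method cannot do the job stated for it.

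This matters because the plan gives these analyses evidential weight. Section 5.7 treats the within-arm result as showing an intervention effect. Section 6.2 offers the within-arm analyses as further efficacy estimates that do not depend on historical controls. The executive summary in section 2 says that comparing accepters with non-accepters is meant to adjust for bias in consent, and section 6.1 counts self-selection among the biases that must be addressed. A result reported as propensity-adjusted would suggest that measured acceptance bias had been handled when, for most of the listed covariates, it had not.

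**Working it through.** The plan states no figure on this point, so there is none to reproduce. The argument follows from the definitions; the numbers only illustrate it.

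**Step 1: the weight.** Let e(x) = P(prospective | X = x), as in section 5.3. Every woman in the contrast is prospective, so her weight is 1/e(x), whether she is a compliant completer (A = 1) or a non-intervention completer (A = 0).

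**Step 2: its effect on balance.** Weighting turns the covariate distribution f(x | A=1) into one proportional to f(x | A=1)/e(x), and f(x | A=0) into one proportional to f(x | A=0)/e(x). Their ratio is f(x | A=1)/f(x | A=0) times a constant, because e(x) cancels. The weighted groups match only if the unweighted groups already did. Truncating the weights at percentiles changes nothing here, because the truncated weight is still a function of x alone.

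**Step 3: the score that would work.** Let a(x) = P(A=1 | x), among the women compared. Weights 1/a(x) and 1/(1 − a(x)) make both distributions proportional to f(x), so they match on the measured covariates.

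**Step 4: which covariates are affected.** Section 5.3 lists 15 candidates for the score and 3 for the primary regression (maternal age, parity, and the substance-use marker). All 3 are on both lists, so 15 − 3 = 12 candidates enter only through the score: race, two BMI variables, height, chronic hypertension, insurance, smoking and others. Those that pass the missing-data rule are the ones left unbalanced.

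**Step 5: illustration.** From section 4: 1,453 prospective women, 10,000 controls and 34% higher-risk (1,453 × 0.34 ≈ 494 women). Assumed: one covariate standing for those that enter only through the score; no treatment effect; acceptance log-odds 0.2 plus 0.5 or 1.0 per SD, so that about half accept; outcome log-odds −2 − 0.7 per SD; prospective arm shifted by 0, +0.3 or −0.3 SD from the controls; arm weights truncated at the 1st and 99th percentiles; means over 60 replicates. SMD is the standardized difference and RD the spurious risk difference, accepters minus decliners.

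| Arm shift | Acceptance slope | SMD: none / plan's score / acceptance score | RD: none / plan's score / acceptance score |
|---|---|---|---|
| 0 | 0.5 | 0.469 / 0.469 / 0.002 | −0.036 / −0.036 / 0.000 |
| 0 | 1.0 | 0.919 / 0.919 / −0.010 | −0.066 / −0.066 / 0.001 |
| +0.3 | 0.5 | 0.476 / 0.478 / −0.003 | −0.032 / −0.036 / 0.000 |
| +0.3 | 1.0 | 0.904 / 0.909 / −0.010 | −0.058 / −0.065 / 0.000 |
| −0.3 | 0.5 | 0.487 / 0.483 / 0.000 | −0.043 / −0.039 / 0.000 |
| −0.3 | 1.0 | 0.918 / 0.925 / 0.016 | −0.074 / −0.068 / −0.001 |

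The plan's score leaves the imbalance where it was. The near-zero last entries are expected, because the only confounder was made measurable.

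**The case against.** The strongest reply is that the plan does not rely on the score alone. The propensity-adjusted version keeps the covariate regression (section 5.4), section 5.7 also runs a separate covariate-adjusted version, and the re-assessment depends on the risk score. All of this stands. A reader might infer that the within-arm estimates carry the whole of the self-selection; the text does not support that. The simulation has no covariate regression beside the weights, so it speaks only for variables confined to the score.

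Three other extensions are tempting and do not hold as stated.

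- **Every within-arm analysis is an accepter-decliner contrast.** The discontinuity is fitted in the mITT population, from which section 5.1 leaves out higher-risk decliners. The steroid comparison inside the arm is higher-risk versus not-higher-risk. In both, group is set by the 16% threshold, and a propensity model containing the risk score would have no overlap. The arm score is of no use there either, but for a different reason.
- **Screening covariates by significance is hopeless in a few hundred women.** The rule beginning "If use of any treatment is significantly associated with variables specified for the alternative analysis" concerns the completers population, which includes historical controls, so small-sample power figures do not describe it. A similar rule for compliance is stated for the compliant-completers analysis, but not for the risk-score re-assessment.
- **Section 6.1 already concedes that the bias cannot be directly adjusted.** Its reason is that historical controls have no risk score. Inside the prospective arm the score exists, so measured acceptance bias can be modelled.

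**Conclusion.** The point holds in a limited form. In the compliant versus non-intervention completers contrast, the prescribed score has the wrong dependent variable and cannot balance the groups. This follows from sections 5.3 and 5.7 without any assumed number. What stays uncorrected is acceptance bias carried by variables that enter only through the score. Its size and direction in this trial cannot be known from the SAP. The simulated risk differences, −0.032 to −0.074 unweighted and −0.036 to −0.068 under the plan's score, rest on assumed effects and should be read as illustrations.

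The mITT discontinuity can carry acceptance bias by another route, since only women who started treatment remain above the threshold. All of this is exploratory. A reader might infer a threat to the co-primary or secondary tests; there is none, because those compare prospective women with historical controls, which is what the score was built for. The change should be made because the plan presents these results as evidence of efficacy.

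**What to change.** - **Compliant versus non-intervention completers** (the risk-score re-assessment, and the comparison of compliers with non-intervention completers elsewhere in section 5.7): replace the arm score with a separate logistic model among higher-risk women. The dependent variable is compliant completer versus non-intervention completer. The predictors are the pre-draw covariates of the section 5.3 alternative list plus the PreTRM risk score, all entered regardless of significance. Weight by this score and require an absolute standardized mean difference below 0.1 between these two groups. State that unmeasured acceptance bias remains.
- **Threshold-defined contrasts** (the discontinuity and the higher- versus not-higher-risk steroid comparison): drop the arm-score version and use covariate adjustment. State that the mITT discontinuity omits higher-risk decliners and so can carry acceptance bias.
- **Contrasts that include historical controls:** keep the prospective-versus-historical score, and only there.

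The cost is SAP wording and one more logistic model on data already collected.

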From historical data on pregnancies at ChristianaCare Health System, we estimated a historical preterm birth rate of 9.1%. The sample size estimation is based on simulations of co-primary outcomes based on a simulated distribution of gestational age with a singleton preterm birth rate of 9.1%, and an effect of intervention based on literature data²⁶⁻²⁸, with α -level spending of 0.05 shared between co-primaries using Holm's method.

Given shut-down of the study due to the SARS-CoV-2 pandemic, the sample size for the study is estimated to be approximately 1,453 subjects in the prospective arm, and approximately 10,000 in the historical control group. In the primary and alternative analyses, more than 10,000 subjects may meet the eligibility criteria for the historical control group and have the required data, and if so, they will be included in the study.

Power and sample size for this study are affected by factors including the proportion of prospective subjects receiving PreTRM® risk scores at or above the threshold of 16% risk (the study Screen Positive Rate (SPR)), the proportion of higher-risk subjects complying with interventions (compliance), and the rate at which subjects and their neonates remain in the study (retention). For the purpose of power and sample size estimation and based on study monitoring, we estimate that 34% of subjects in the pre-pandemic portion of the prospective arm had PreTRM® risk scores at or above the threshold of 16% risk (the SPR).

Power and sample size are also affected by the study population's baseline level of risk of adverse neonatal outcomes related to prematurity, the sensitivity of testing in identifying at-risk pregnancies, retention of subjects in the study and the efficacy of the interventions as implemented in the study. Literature²⁶⁻²⁸ indicates that the effect of treatment is not constant across different values of GAB. Thus, there is no single value of the effect size in terms of proportion of subjects with NMI less than 3, or mean length of stay. Rather, the effect size is larger for subjects with earlier GAB, while the effect size is reduced for subjects with later GAB.

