For these reasons, power and sample size were estimated based on simulations, using a range of possible values for the factors noted above. These simulations used the observed distribution of GAB from previous studies, adjusted to match the expected overall preterm birth rate of 9.1% in this study. Treatment effect was modeled as a shift in the GAB corresponding to the effect sizes reported in published studies of preterm birth prevention that were based on single treatment modalities, and with extrapolated treatment effects estimating additive effects of bundled interventions.

For the first co-primary endpoint, reduction of severe composite morbidity/mortality, a range of the possible expected effect size can be inferred from the simulations. In the simulations, the proportion of subjects with NMI ≥ 3 is expected to be between 0.023 and 0.02 in the prospective arm and near 0.036 in the control arm based on a previous clinical utility study (Sera Prognostics: data on file). Assuming these proportions, a one-

sided Fisher's Exact test, a sample size of approximately 1,453 subjects with outcomes in the prospective arm with 55% compliance among higher risk subjects and about 10,000 historical controls provides power of 0.7 – 0.9 (NCSS PASS 2020, module "Group-Sequential Tests for Two Proportions").

For the second co-primary test, length of neonatal hospital length of stay from time of birth up to neonatal discharge is assessed by Cox proportional hazards regression with stratification. The hazard ratio based on simulations is expected to be between 1.32 and 1.46 based on a previous clinical utility study (Sera Prognostics: data on file). Assuming these hazard ratios, a sample size of approximately 1,453 subjects with outcomes in the prospective arm with 55% compliance among higher risk subjects and about 10,000 historical controls provides power of 0.8 – 1.0 (NCSS PASS 2020, modules "Group-Sequential Tests for Two Hazard Rates" and "Tests for Two Survival Curves Using Cox's Proportional Hazards Model"). Stratification is indicated based on non-proportionality observed in previous studies.

The two co-primary endpoints provide independent measurements of improved neonatal outcomes. Due to their correlation, there may be modest power to be gained from having two co-primary endpoints. The estimated study power for the combination of the two co-primary endpoints is 0.8 – 1.0.

5 Statistical Analysis

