- a) The higher-risk group will be compared to the not-higher-risk group within the prospective arm, for tests of equivalence. This comparison is independent of any selection biases or epoch effects present in comparisons of the prospective arm relative to historical controls.
- b) The not-higher-risk group of the prospective arm will be compared to historical controls to assess test sensitivity. It is expected that there will be significant differences in baseline characteristics between the two groups. The analysis will be performed without adjustment, adjusted for covariates specified for the primary analysis, and adjusted via propensity scoring as specified for the alternative analysis.
- c) The higher-risk group in the prospective arm will be compared to a control comparator group estimated as the difference between the control group and the not-higher-risk group, to assess efficacy of the intervention strategy. For count endpoints, direct subtraction of counts (adjusted for arm size) will be used to estimate the comparator group. For non-count endpoints, a number of most similar outcomes proportional to arm size will be removed from the control comparator group for each subject in the not-higher-risk group. It is expected that there will be significant differences in baseline characteristics between the two groups. The analysis will be performed without adjustment, adjusted for covariates specified for the primary analysis, and adjusted via propensity scoring as specified for the alternative analysis.

The following exploratory outcomes will be examined using only the descriptive statistics described above.

- Birthweight
- Number of days of mechanical ventilation

- Amount of surfactant administered
- Occurrence of birthweight <1500g and <2500g
- Individual components of composite morbidity/mortality index
- Whether or not a neonate received surfactant
- Occurrence of pneumonia
- Occurrence of 5-minute Apgar<7
- Occurrence of asphyxia
- Occurrence of preeclampsia
- Occurrence of gestational diabetes mellitus
- Rate of PPROM
- Rate of preterm delivery not associated with PPROM
- Baseline and on-treatment progesterone levels determined by LC-MS

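### Exploratory comparison (c) plans covariate and propensity adjustment of a comparator left over after subtraction, where adjustment is not valid, and gives no method to carry the sampling error of the subtraction

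*SAP*

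**What the plan says.** Comparison (c) in section 5.7 sets the higher-risk group of the prospective arm against a comparator "estimated as the difference between the control group and the not-higher-risk group, to assess efficacy of the intervention strategy". Two constructions are given:

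- Count endpoints: "For count endpoints, direct subtraction of counts (adjusted for arm size) will be used to estimate the comparator group".
- Other endpoints: "a number of most similar outcomes proportional to arm size will be removed from the control comparator group for each subject", where the subjects meant are the not-higher-risk women.

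The SAP expects baseline differences between the two groups. It plans the analysis unadjusted, "adjusted for covariates specified for the primary analysis, and adjusted via propensity scoring as specified for the alternative analysis". The list that contains (c) is introduced by "The primary, secondary and exploratory endpoints will be applied to comparisons within the mITT population".

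No variance, confidence interval or resampling method is given for the constructed comparator. The one bootstrap in section 5.7 resamples historical controls down to the size of the prospective arm, and it applies to the primary and alternative analyses. Section 4 gives the sizes: "approximately 1,453 subjects in the prospective arm, and approximately 10,000 in the historical control group". It also states "we estimate that 34% of subjects in the pre-pandemic portion of the prospective arm had PreTRM® risk scores" that reached the threshold, and bases power on a prospective arm "with 55% compliance among higher risk subjects and about 10,000 historical controls".

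**The concern.** The comparator is not a sample of women. It is an estimate formed from two samples, and one of them is small. Two problems follow.

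The first is adjustment. Regression with covariates and inverse propensity weights both need individual records with meaningful covariates. The construction either leaves no records or leaves records chosen by their outcome.

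The second is uncertainty. If not-higher-risk counts are scaled up to the control arm before subtraction, their sampling error is scaled up with them. An ordinary test on the remainder would ignore that.

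At stake is one exploratory, control-based estimate of efficacy in higher-risk women. Its adjusted versions could be reported as bias-corrected when they are not, and its intervals could be too narrow.

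**Working it through.** **Adjustment (no figures needed)**

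- *Count endpoints.* Control count minus scaled not-higher-risk count is a single number. It has no age, parity or propensity score attached. The logistic regression that section 5.7 names for proportion endpoints, and the weights 1/PS and 1/(1−PS) of section 5.3, have nothing to act on.
- *Other endpoints.* Real controls remain, but they were kept because their outcomes were unlike those of not-higher-risk women. Their covariates are those of controls selected on outcome, not of women who would have tested higher-risk. Many outcomes are also tied: section 3.7 sets NICU stay to zero for every baby admitted to hospital but never to the NICU. The SAP has no rule for which tied control is removed, so the covariate mix of the remainder is not determined.

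**Uncertainty: inputs**

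The SAP states no standard error, power or sample size for (c), so there is no figure to reproduce.

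- From section 4: 10,000 controls, 1,453 prospective women, s = 0.34, control rate of NMI ≥ 3 of 0.036, preterm birth rate 0.091.
- Derived: higher-risk 0.34 × 1,453 = 494; not-higher-risk 1,453 − 494 = 959; treated higher-risk 0.55 × 494 = 272. The last takes 55% compliance as mITT membership, which is an assumption.
- Assumed: S, the share of events that fall in higher-risk women, 0.60 to 0.85. The SAP does not give it.
- Scale-up reading: 10,000/1,453 = 6.9 controls per not-higher-risk woman. That removes about 959 × 6.88 = 6,600 and leaves about 3,400.

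**Formulas** (no intervention effect, correct scaling)

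- Rates: p_N = (1−S)·p_C/0.66 and p_H = S·p_C/0.34
- True comparator SE = √[p_C(1−p_C)/10,000 + 0.66²·p_N(1−p_N)/959] / 0.34
- Naive comparator SE = √[p_H(1−p_H)/3,400]
- For the comparison, add p_H(1−p_H)/272 to each variance.

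**Worked case: NMI ≥ 3, S = 0.60**

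- p_N = 0.40 × 0.036/0.66 = 0.0218; p_H = 0.60 × 0.036/0.34 = 0.0635.
- True SE = √(3.47×10⁻⁶ + 9.69×10⁻⁶)/0.34 = 0.0107. Naive SE = 0.0042. Ratio 2.55.
- SE of the treated group's rate = √(0.0635 × 0.9365/272) = 0.0148.
- Comparison: true √(0.0107² + 0.0148²) = 0.0182; naive √(0.0042² + 0.0148²) = 0.0154. Ratio 1.19.

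**Range, with simulated rejection of a pooled z-test at nominal 5%, 272 treated**

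| Endpoint, S | Comparator SE, true/naive | Comparison SE, true/naive | One-sided, favouring intervention | Two-sided | Two-sided if scaled down to 494 |
|---|---|---|---|---|---|
| NMI ≥ 3, 0.85 | 1.60 | 1.06 | 5.3% | 6.4% | 2.6% |
| NMI ≥ 3, 0.60 | 2.55 | 1.19 | 6.9% | 10.1% | 4.9% |
| Preterm birth, 0.85 | 1.71 | 1.07 | 6.0% | 6.7% | 2.8% |
| Preterm birth, 0.60 | 2.64 | 1.20 | 7.8% | 10.4% | 5.1% |

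The comparator ratio depends on S. If the test carried no information (S = 0.34), it would reach about 4.0.

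**Which share is used**

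If arm size means the mITT arm, the higher-risk share becomes 272/(959 + 272) = 0.22 instead of 0.34. Take p_N at half the control rate, 0.018. The comparator rate should be (0.036 − 0.66 × 0.018)/0.34 = 0.071. With mITT shares it becomes (0.036 − 0.779 × 0.018)/0.221 = 0.100, which favours the intervention.

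**The case against.** **The large ratio belongs to the comparator alone.** This stands. A reader might infer that the standard error of comparison (c) is 1.6 to 2.6 times too small. It is not: the 272 treated women dominate the variance, and the shortfall is about 5 to 20%.

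**The scaling is not stated.** This stands too. The count sentence says only that arm size is adjusted for. Removing a number of controls proportional to arm size for each not-higher-risk woman points to scale-up, but does not settle it for counts. Under scale-down the naive test is nominal or conservative, so one cannot say that error rates exceed nominal under every correct scaling.

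**Treating the remainder as observed is an inference.** The SAP names no test or sample size for (c). The inference rests on its naming ordinary regression and propensity methods and no other source of variance.

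**One-sided tests are the relevant ones.** The SAP makes primary and secondary tests one-tailed and words the exploratory alternatives directionally. The smaller, one-sided excess is therefore the fairer figure.

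**Weighting could come first.** Propensity-weighting the controls before subtracting counts is feasible and would be sound. The SAP does not say that this is meant: it describes adjusting the comparison of the two groups. The same reading does not rescue deletion by outcome.

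**Using all 494 higher-risk women gives about 14% two-sided rejection.** That needs every higher-risk woman to have started treatment, which conflicts with the 55% assumption and the mITT definition.

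**The analysis is exploratory.** Section 5.7 also offers the risk-score discontinuity and the compliant-completer analyses. This limits the consequence but does not make the stated method valid.

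**Conclusion.** The point holds in two parts.

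The firmer part needs no assumed figure. Adjustment after subtraction is not valid: count endpoints leave no records, and other endpoints leave controls selected on the outcome.

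The second part is that the SAP gives no way to carry the sampling error of about 959 not-higher-risk women. Its size is conditional on scale-up to about 3,400 controls, on 60 to 85% of events falling in higher-risk women, and on 272 treated women. The comparator's own standard error is then about 1.6 to 2.6 times too small and that of the comparison about 1.05 to 1.20 times. Nominal 5% rejection is about 5 to 8% one-sided and 6 to 10% two-sided. Under scale-down to about 494 it is about 2.6 to 5.1% two-sided.

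A reader might go further and conclude that the adjusted results mean nothing under any reading, or that the trial's efficacy case rests on this analysis. The documents support neither. Weighting before subtraction would be meaningful if specified, and (c) is one of several exploratory efficacy analyses. It should still be corrected, because followed as written it gives an invalid adjusted estimate.

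**What to change.** Rewrite comparison (c) as follows:

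- Estimate the untreated higher-risk rate as (r_control − (1−s) × r_not-higher)/s. Take s as the observed screen-positive rate among all tested women (about 0.34), not the higher-risk share of the mITT population.
- Standardise or weight the controls to the covariates of the whole tested prospective arm before subtracting.
- Obtain the confidence interval by bootstrapping controls and prospective subjects jointly through the whole calculation, including s.
- Delete the outcome-matched removal of controls and any covariate or propensity adjustment after subtraction.

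The cost is SAP wording, a bootstrap and generally wider intervals. No new data are needed. The change does not remove self-selection among higher-risk women who accept treatment, which section 6.1 already acknowledges.
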